#### 4.1.13. Handling of Alphanumeric Data

Should there be instances where a clinical laboratory parameter is reported with imbedded non-numeric characters, as for example, “<0.1” or “>10”, the data will be imputed for quantitative summaries. The actual values as reported in the database will be presented in data listings.

For incorporation in quantitative summaries (except for concentration data), the following imputation rules will be employed:

- The lower limit of quantification will be replaced with  $\frac{1}{2}$  the value of the lower limit. For example, < 0.1 will be replaced with 0.05.
- The upper limit of quantitation will be increased by one level of precision that precedes the value. For example, “>0.1” will be imputed to “0.11”, and “>10” will be imputed to “10.1”.

Additionally, the upper limit of normal (ULN)/lower limit of normal (LLN) values may be reported as alphanumeric (e.g., ‘<5’, ‘≤5’, ‘>5’, ‘≥5’). In these cases, if the ULN or LLN is necessary for determination of the laboratory severity grade, the following conventions will be employed:

If the value is in the form of  $\leq 5$ , the ULN will be populated with the value after removing the symbol (i.e., the ULN is set to 5). If the value is in the form of <5, the ULN will be decreased by two levels of precision in the direction of the symbol (i.e., the ULN is set to 4.99).

If the value is in the form of  $\geq 5$ , the LLN will be populated with the value after removing the symbol (i.e., the LLN is set to 5). If the value is in the form of  $>5$ , the LLN will be increased by two levels of precision in the direction of the symbol (i.e., the LLN is set to 5.01).

## 4.2. Analysis Visit Windows

Data collected longitudinally across visits will be summarized and analyzed by visit.

Assessments made on scheduled visits will be mapped to an appropriate analysis visit that corresponds to the nominal visit. Early termination and unscheduled visits will be assigned to visit windows based on the study day of the event. For unscheduled and early termination vital signs, timepoint will be windowed. For unscheduled and early termination vital signs that occur on study day 1, the time of the last scheduled pre-dose triplicate on Day 1 (nominal visit) will be used to determine if the timepoint should be windowed to a pre-dose or post-dose timepoint. For all other study days, the timepoint will be assumed to be post-dose.

**Table 2: Analysis Visit Window**

Study Day of Early Termination or Unscheduled Visit	Analysis Visit	Analysis Visit Target Day
PANSS and CGI-S		
$\leq 1$	Baseline	1
2-10	Week 1	7
11-17	Week 2	14
18-24	Week 3	21
25-31	Week 4	28
32-38	Week 5	35
$\geq 39$	Week 6	42
ECGs and C-SSRS		
$\leq 1$ (before Day 1 assessment + 1 hour)	Baseline	1
2-10	Week 1	7
11-17	Week 2	14
18-24	Week 3	21
25-31	Week 4	28
32-40	Week 5	35
$\geq 41$	Week 6	45
Blood Pressure and Heart Rate		
$\leq 1$ (before Day 1, Pre-Dose assessment)	Baseline	1
1 (after Day 1, Pre-Dose assessment)	Day 1	1
2-10	Week 1	7

Study Day of Early Termination or Unscheduled Visit	Analysis Visit	Analysis Visit Target Day
11-17	Week 2	14
18-24	Week 3	21
25-31	Week 4	28
32-40	Week 5	35
≥ 41	Week 6	45
Respiratory Rate and Temperature		
≤ 1 (before Day 1, Pre-Dose assessment)	Baseline	1
2-10	Week 1	7
11-17	Week 2	14
18-24	Week 3	21
25-31	Week 4	28
32-40	Week 5	35
≥ 41	Week 6	45
Extrapyramidal Symptoms (SAS, AIMS, BARS), Laboratory Assessments (Chemistry, Hematology, Urinalysis, and Coagulation) and Weight		
≤ 1	Baseline	1
2 - 32	Week 3	21
≥ 33	Week 6	45
CGI-I		
1 - 32	Week 3	21
≥ 33	Week 6	42
BACS, SF-6D, and Laboratory Assessments (Prolactin and Urine Pregnancy Test)		
≤ 1	Baseline	1
≥ 2	Week 6	45

If assessments are collected multiple times within a given visit window, the scheduled visit, if available, will be used for summary presentations. If no scheduled visit is available, then the result closest to the scheduled visit date will be used for summary presentations. If two unscheduled measurements (early termination or unscheduled visit) have the same distance to the target date, the later value will be used. If a subject has multiple non-missing unscheduled values on the same date, then the last one is used, as determined by the time collected, if available.

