1.2 Schema

Figure 1 Trial Schematic

Abbreviations: QD=once daily; R=randomization.

Note: Assessment time points are planned for the last day of the indicated week (eg, Day 7, 14, 21, etc) with a ± 2 day window (see Schedule of Assessments in [Section 1.3](#)).

- Participants will be admitted to the inpatient facility at the time they sign the ICF and remain in the inpatient facility for the duration of treatment.
- Extension of screening (up to a maximum of 21 days total) is allowed following discussion and documented approval by the medical monitor prior to the expiration of the Screening Period.

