###### 3.1.1.3. Derivation of PANSS Proportion of Responders

The number and proportion of responders is defined as subjects with 30% reduction from Baseline in the PANSS total score at Week 6 or the early termination visit.

For subjects who discontinue and do not have an early termination visit, the subject's last assessment will be considered.

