### **3.1.2.1. Derivation of CGI-S Proportion of Responders**

The number and proportion of responders is defined as the following:

- Subjects having  $\geq 1$ -point improvements from Baseline in CGI-S score at the Week 6 visit or the early termination visit. For subjects who discontinue and do not have an early termination visit, the subject's last assessment will be considered.
- Subjects having  $\geq 2$ -point improvements from Baseline in CGI-S score at the Week 6 visit or the early termination visit. For subjects who discontinue and do not have an early termination visit, the subject's last assessment will be considered.

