### **5.9.2. Main Analytical Approach**

The change from baseline to each study visit in total PANSS score will be summarized by visit and treatment group. A MMRM analysis will be used to analyze the data from all post-randomization timepoints up to Week 6 with treatment, geographic region, visit, and treatment by visit interaction as fixed effect, subject as a random effect, and baseline PANSS score as a covariate. An unstructured covariance structure will be used for the repeated measures. If the unstructured covariance matrix results in convergence issue, the heterogeneous Toeplitz covariance structure followed by the heterogeneous first-order autoregressive (AR(1)) structure will be used. The Kenward-Roger approximation will be used to estimate the denominator degrees of freedom. The difference between each emraclidine dose group and placebo at Week 6 will be estimated based on the Least Squares Mean (LSMean) difference between the treatment groups at Week 6 from the MMRM with the associated 95% confidence interval (CI) and P-value. A Cohen's D value will be derived as the ratio of the estimated difference to the population standard deviation at each visit estimated from the model (the square root of the diagonal elements of the estimated covariance matrix). The missing values are assumed to be missing at random for the main analysis, including missing due to missed visits or early termination due to COVID-19 control measures. The LSM ( $\pm$ SE) from the model will be plotted for change in PANSS total score by visit and treatment group. Similarly, the mean ( $\pm$ SD) of absolute values and change from Baseline PANSS total score will be presented by visit and treatment group.

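### SAP 4.2 keeps the scheduled PANSS or CGI-S score over a later early-termination score in the same window, so the last score before dropout can be left out of the MMRM

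*SAP*

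**What the plan says.** SAP section 4.2 opens: "Data collected longitudinally across visits will be summarized and analyzed by visit". Scheduled visits keep their nominal visit, and "Early termination and unscheduled visits will be assigned to visit windows based on the study day of the event". For PANSS and CGI-S, Table 2 gives Days 2–10 to Week 1, 11–17 to Week 2, 18–24 to Week 3, 25–31 to Week 4, 32–38 to Week 5, and Day 39 onward to Week 6, with targets at Days 7, 14, 21, 28, 35 and 42. The text under the table says: "If assessments are collected multiple times within a given visit window, the scheduled visit, if available, will be used for summary presentations". A separate tie rule covers only unscheduled records: "If two unscheduled measurements (early termination or unscheduled visit) have the same distance to the target date, the later value will be used".

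The primary model in SAP 5.9.2 is by visit with unstructured covariance: "A MMRM analysis will be used to analyze the data from all post-randomization timepoints up to Week 6". SAP 5.10.2 does the same for CGI-S. Protocol 1.2 says that assessments are "planned for the last day of the indicated week (eg, Day 7, 14, 21, etc) with a ± 2 day window".

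Three other places bear on the point:
- The responder analyses name the ET visit. PANSS responders (SAP 3.1.1.3) are "subjects with 30% reduction from Baseline in the PANSS total score at Week 6 or the early termination visit". The CGI-S definition (3.1.2.1) does likewise, with a fallback: "For subjects who discontinue and do not have an early termination visit, the subject's last assessment will be considered".
- Protocol 9.3.2 uses a treatment policy strategy in which every outcome gathered counts, except data under a prohibited antipsychotic. SAP 5.11 uses a hypothetical strategy and censors data once treatment has been discontinued.
- Protocol 7.2 and the schedule of assessments ask for ET assessments before antipsychotics restart where possible, and say that the efficacy scales should not be done afterwards.

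**The concern.** Each PANSS or CGI-S window for Weeks 1 to 5 runs three days past its target. A patient rated on schedule who leaves within those days gives two records in one window, and the rule keeps the earlier one. The MMRM can take only one record per patient and visit, and this is the only selection rule given, so the score recorded at dropout goes unused. Whether it counts depends on the calendar and not on its content.

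The main analysis assumes data missing at random given the observed scores. When dropout follows a sudden worsening, the ET score is the observation that makes this assumption plausible. Without it, the model projects Week 6 from a score taken before the worsening, and the arm with more such dropouts looks better than it should. The primary and key secondary comparisons are at stake, as are the other by-visit PANSS and CGI-S analyses.

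**Working it through.** **1. The plan's own figures.** The plan states no share of ET scores affected. Its sample size reproduces: n per arm = 2(1.960 + 1.282)²/0.48² = 91.2, so 92; power with 93 is 0.905 (0.903 with the noncentral t). Then 93/0.75 = 124 per arm and 3 × 124 = 372. Planned discontinuers are 372 − 279 = 93, or 31 per arm. The sample size is not in question.

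**2. Example.** Week 2 PANSS is done on Day 14, and the patient leaves on Day 16 with an ET PANSS. Day 16 lies in 11–17, which already holds a scheduled score, so the Day 14 score is used. Two days later, Day 18 would fall in 18–24 and the ET score would be kept as Week 3.

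**3. Days affected.** For a window ending on day U with target T, and visits shifted by s days, the affected days number U − (T + s). U − T = 3 for each of Weeks 1 to 5, so the total is 5(3 − s), set against the 40 days from Day 2 to Day 41.

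| Every visit | Days | Share |
|---|---|---|
| 2 days early | 25 | 62.5% |
| 1 day early | 20 | 50% |
| on target | 15 | 37.5% |
| 1 day late | 10 | 25% |
| 2 days late | 5 | 12.5% |

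On target, these are Days 8–10, 15–17, 22–24, 29–31 and 36–38. Independent shifts, uniform within ±2 days, average 15 days (37.5%). An ET rating before that window's scheduled visit is kept. One on Days 43–45 after a Day 42 PANSS does not change the Week 6 record.

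**4. Illustration in patients.** If dropout days were uniform and all 93 discontinuers had an ET rating, 93 × 0.375 ≈ 35 scores would go unused (31 × 0.375 ≈ 12 per arm), with a range of 93 × 0.125 ≈ 12 to 93 × 0.625 ≈ 58. Both conditions are assumptions.

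**5. Bias at Week 6.** Suppose a fraction p of an arm drops out after a persistent worsening of D points, and a share q of those ET scores goes unused. If the model would have carried the whole worsening to Week 6, the bias toward zero is about (p_placebo − p_active) × q × D. Assume p of 15–20% on placebo and 5–10% on active, D of 10–20 points, and q = 0.375:
- smallest contrast: (0.15 − 0.10) × 0.375 × 10 = 0.19 points
- largest contrast: (0.20 − 0.05) × 0.375 × 20 = 1.13 points

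The result is zero if D = 0 or the two fractions are equal, and it scales with q.

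Two sets of simulations of the by-visit likelihood analysis with these p and D (1,240 per arm, 60 replicates) gave 0.25–1.0 and 0.36–1.21 points. A further set, also with abrupt worsening commoner on placebo, gave 0.25–0.6 under the present rule and −0.2 to 0.2 when the ET score was kept. With gradual worsening only, the bias was 0.04–0.08. That is no larger than the Monte Carlo error of √(2 × 14.5²/1240)/√60 ≈ 0.08 (unpaired runs).

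**6. Sensitivity analyses.** The imputations in SAP 5.9.3.2 and 9.6 start from the retained records. The delta shift applies only to the active arms, and placebo cases classed as not missing at random are imputed as missing at random. An unused placebo score is therefore not recovered.

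**The case against.** The rule is worded for summary presentations, so applying it to the MMRM is an inference. The inference is strong, because section 4.2 covers analysis as well as summary and no other rule exists. If another rule is intended, it is not prespecified.

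The convention is fixed in advance and identical in all arms, and in the scenario examined the bias is toward zero, hence conservative. This limits the harm, but a conservative bias still costs power against a planned difference of 7 to 8 points.

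The censoring in SAP 5.11 could remove an ET rating made after the last dose whatever section 4.2 says. This stands: changing 4.2 alone may not bring the score in. Yet Table 2 has windows for ET PANSS and CGI-S ratings, which suggests that they are meant to be used.

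The ET visit is asked for only if possible, and the scales are not done once an antipsychotic has started. Patients who worsen most may have no ET score. This also stands, and it lowers the count in step 4.

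A reader might infer that over a third of dropouts lose their last score, or that the score disappears from the trial's efficacy results altogether. The documents support neither. They give no distribution of dropout times, so 37.5% is a share of days only, and the PANSS and CGI-S responder analyses use the ET score.

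**Conclusion.** The point holds for the by-visit PANSS and CGI-S analyses. The multiple-record rule, not the tie rule, sets aside an ET score rated after that window's scheduled visit, and this sits badly with protocol 9.3.2. The share of days rests on Table 2 and on visits kept close to target; it falls below a third if visits run a day or more late.

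The bias of a few tenths of a point to about 1 point is assumption-driven: abrupt, persistent worsening at dropout, commoner on placebo, with ET ratings obtained. None of these inputs comes from the documents. By the formula in step 5, the opposite imbalance would reverse the sign and favour the drug, but that case was not simulated. A reader should not infer that the primary result is materially biased as planned. This is a change worth making because it is cheap, not a flaw that invalidates the analysis.

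**What to change.** Add to SAP 4.2, for PANSS and CGI-S:

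> For the MMRM and the imputation analyses, if an early-termination assessment falls in the same window as, and after, a scheduled assessment for Weeks 1–5, the early-termination assessment is the record for that visit; a scheduled Week 6 assessment is kept.

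Keep the present rule for other unscheduled visits. State in SAP 5.9.1 and 5.11 that an ET rating made before any prohibited antipsychotic is not censored as data after treatment discontinuation, and reconcile this with protocol 9.3.2.

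Moving the ET score to the next scheduled visit is tempting but worse. It would turn ratings on Days 36–38 into Week 6 values and could make those dropouts Endpoint completers. No ET score should be moved into Week 6 from an earlier window or define an Endpoint completer.

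The cost is one sentence and two clarifications before unblinding, using data already collected. The earlier scheduled score in that window is then not used for that visit, and the record can lie up to 3 days past the target. Table 2 already accepts wider gaps: an ET rating on Day 2 counts as Week 1, 5 days before its target.

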## 5. STATISTICAL ANALYSIS METHODS

### 5.1. GENERAL CONSIDERATIONS

Descriptive statistical methods will be used to summarize the data from this trial, with statistical testing performed for the efficacy endpoints. Unless stated otherwise, the term “descriptive statistics” refers to number of subjects (N), number of observations (n), arithmetic mean, median, standard deviation (SD), coefficient of variation (CV%) (for concentration data only), first quartile (Q1), third quartile (Q3), minimum, and maximum for continuous data, and frequencies and percentages for categorical data. Certain figure presentations will include the standard error of the mean (SE). The term “treatment group” refers to treatment assignment: treatment with 15 mg QD emraclidine, treatment with 30 mg emraclidine or placebo. All data collected from subjects who sign the informed consent form, including screen failures, will be included in data listings. Unless otherwise noted, the data listings will be sorted first by treatment group and subject number and then by date within each subject number.

The statistical analyses will be conducted with the SAS® software package version 9.4 or higher.

### 5.2. Populations for Analyses

The analysis populations are defined (Table 3). [REDACTED]

[REDACTED]

[REDACTED]

**Table 3: Populations for Analysis**

Population	Description	Analysis
All Subjects Screened	All subjects who signed informed consent.	Disposition summary, Inclusion/Exclusion Criteria listings, and Demography listings
ITT	All randomized subjects	Demographic and Baseline Characteristics summaries, Patient History listings
FAS	All randomized subjects who receive at least 1 dose of IMP. This will be the safety analysis set.	Safety analysis
mITT	All randomized subjects who receive at least 1 dose of IMP and have both a baseline and at least 1 postbaseline PANSS assessment	Primary analysis set for efficacy
[REDACTED]	[REDACTED]	Demographic and Baseline Characteristics summaries, select safety and efficacy outputs
Endpoint completers	All subjects in the mITT population who complete the PANSS assessment at Week 6	Sensitivity analysis for efficacy
PK Analysis Set	All randomized subjects who receive at least 1 dose of IMP and have at least 1 measurable emraclidine concentration	PK analysis

Abbreviations: FAS=full analysis set; IMP=investigational medicinal product; ITT=intent-to-treat; mITT=modified intent-to-treat; PANSS=Positive and Negative Syndrome Scale; PK=pharmacokinetic.

### 5.3. Statistical Hypotheses

[figure not shown]
The primary hypotheses are summarized below. The tests will be conducted in hierarchical order from  $H_1$  to  $H_2$  at a 2-sided  $\alpha$  level of 0.05. If both primary hypotheses  $H_1$  and  $H_2$  are successful, the key secondary endpoint of change from baseline CGI-S at Week 6 will be similarly tested in hierarchical order with respect to the 2 doses. The overall type I error rate thus is maintained at the 0.05 level.

Primary Endpoint	Emraclidine 30 mg QD vs Placebo	Emraclidine 15 mg QD vs Placebo
Change from Baseline to Week 6 in PANSS total score	$H_1 : \mu_{\text{active}} = \mu_{\text{placebo}}$ vs $\mu_{\text{active}} \neq \mu_{\text{placebo}}$	$H_2 : \mu_{\text{active}} = \mu_{\text{placebo}}$ vs $\mu_{\text{active}} \neq \mu_{\text{placebo}}$
Secondary Endpoint	Emraclidine 30 mg QD vs Placebo	Emraclidine 15 mg QD vs Placebo
Change from Baseline to Week 6 in CGI-S total score	$H_3 : \mu_{\text{active}} = \mu_{\text{placebo}}$ vs $\mu_{\text{active}} \neq \mu_{\text{placebo}}$	$H_4 : \mu_{\text{active}} = \mu_{\text{placebo}}$ vs $\mu_{\text{active}} \neq \mu_{\text{placebo}}$

Abbreviations: PANSS=Positive and Negative Syndrome Scale; QD=once daily; CGI-S=Clinical Global Impression-Severity of Symptoms Scale

## 5.4. Multiplicity Adjustment

A graphical approach depicted below illustrates the hierachal multiple testing strategy planned for the hypotheses described above to control the overall Type I error rate. The primary endpoint of the emraclidine 30 mg QD will be compared with that of placebo ( $H_1$ ) with full  $\alpha$  of 0.05 and, if successful, the available  $\alpha$  will be passed along fully ( $r=1$ ) to the comparison of the primary endpoint of emraclidine 15 mg QD with placebo ( $H_2$ ). If  $H_2$  is successful, the full  $\alpha$  will be available to the secondary hypothesis  $H_3$ . The sequence will continue until  $H_4$  or until the sequence breaks with no  $\alpha$  remaining available.

## 5.5. Strata and Covariates

Randomization was stratified by geographic region with two strata: United States or Other Countries.

The baseline value of each efficacy variable will be included as a covariate in the efficacy analyses.

## 5.6. Subject Disposition, Demographic and Baseline Characteristics

Subject disposition will be based on the ITT population with tabulation of the number of subjects who complete the study and the number of subjects discontinued from the study and the reasons by treatment group. Additionally, the number of days on study will be summarized.

Further tabulation by region (United States, Other Countries) and country will also be presented. Subject disposition data will also be tabulated for all subjects screened to include the number of subjects screened, the number of screen failures, and the reason for screen failure.

Number of subjects in each analysis population set will be summarized.

Additionally, the number of subjects randomized at each site and overall will be summarized by country, treatment group, and overall. Summaries will be presented for randomized subjects and completed subjects.

Demographic data and baseline characteristics including age, age group, sex, fertility status, race, ethnicity, smoking status (smoker vs. non-smoker) at Baseline, height at screening, weight at screening and baseline, BMI at screening and baseline, will be summarized using descriptive statistics for the ITT population. Further tabulation by region and country also will be presented.

Baseline disease characteristics including time (years) since diagnosis of schizophrenia, number of hospitalizations in the last 5 years, PANSS total score at Baseline, PANSS positive subscale score at Baseline, PANSS negative subscale score at Baseline, PANSS Marder Negative score at Baseline, PANSS delusions score at Baseline, PANSS conceptual disorganization score at Baseline, PANSS hallucinatory behavior score at Baseline, PANSS suspiciousness/persecution score at Baseline, CGI-S score at Baseline, change in PANSS total score from Screening to Baseline (Screening – Baseline), and percent change in PANSS total score from Screening to Baseline will be summarized by treatment group. Further tabulation by region and country also will be presented.

## 5.7. Medical and Psychiatric History

Medical and psychiatric history events will be mapped to a Medical Dictionary for Regulatory Activities (MedDRA) version 26.0 or higher by preferred term and system organ class. Medical and psychiatric history will be summarized by treatment group using preferred terms and system organ classes. All events will be listed.

